### **5.4 Treatment blinding**

Patients, investigational staff, persons performing the assessments, Novartis clinical trial team and their agents, central laboratory, central imaging and data analysts will remain blinded to the identity of the treatment from the time of randomization until database lock, using the following methods: (1) Randomization data are kept strictly confidential until the time of unblinding, and will not be accessible by anyone else involved in the study, (2) the identity of the treatments will be concealed by the use of study drugs that are all identical in packaging, labeling, schedule of administration and appearance.

Unblinding will only occur in the case of patient emergencies (see [Section 5.5.9](#)) and at the conclusion of the study.

### **5.5 Treating the patient**

Sponsor qualified medical personnel will be readily available to advise on trial related medical questions or problems.

#### **5.5.1 Patient numbering**

Each patient is uniquely identified in the study by a combination of his/her center number and patient number. The center number is assigned by Novartis to the investigative site. Upon signing the informed consent form, the patient is assigned a patient number by the investigator. At each site, the first patient is assigned patient number 00001, and subsequent patients are assigned consecutive numbers (e.g. the second patient is assigned patient number

00002, the third patient is assigned patient number 00003). The investigator or his/her staff will contact the IRT and provide the requested identifying information for the patient to register them into the IRT. Only the assigned patient number should be entered in the field labeled “Patient ID” on the EDC data entry screen (e.g. enter ‘00001’, ‘00002’, etc.). Once assigned to a patient, the patient number will not be reused. If the patient fails to be randomized for any reason, the IRT must be notified within 2 days that the patient was not randomized. The reason for not being randomized will be entered on the Screening Log, and the Demography CRF pages should also be completed. The patient numbers are already created into eCRF. This patient number should be used in all documents or request forms for vendors.

e.g.: site 0001 patient number 00002 will have the subject number 000100002.

Additional information to be collected on Screening Failures is described in [Section 6.1](#). A patient who is rescreened should be assigned the next consecutive number.

## **5.5.2 Dispensing the study drug**

Each study site will be supplied with study drug in packaging of identical appearance.

The study medication packaging has a 2-part label. A unique randomization number is printed on each part of this label which corresponds to one of the 2 treatment arms. Investigator staff will identify the study drug package to dispense to the patient by calling the IRT and obtaining the medication number. Immediately before dispensing the package to the patient, the investigator staff will detach the outer part of the label from the packaging and affix it to the source document (Drug Label Form) for that patient’s unique patient number.

## **5.5.3 Handling of study and additional treatment**

### **5.5.3.1 Handling of study treatment**

Study treatment must be received by a designated person at the study site, handled and stored safely and properly, and kept in a secured location to which only the investigator and designees have access. Upon receipt, all study treatment must be stored according to the instructions specified on the labels. Clinical supplies are to be dispensed only in accordance with the protocol. Technical complaints are to be reported to the respective Novartis CPO Quality Assurance.

Medication labels will be in the local language and comply with the legal requirements of each country. They will include storage conditions for the study treatment but no information about the patient except for the medication number.

The investigator must maintain an accurate record of the shipment and dispensing of study treatment in a drug accountability log. Monitoring of drug accountability will be performed by monitors during site visits or remotely and at the completion of the trial. Patients will be asked to return all unused study treatment and packaging at the end of the study or at the time of discontinuation of study treatment.

At the conclusion of the study, and as appropriate during the course of the study, the investigator will return all unused study treatment, packaging, drug labels, and a copy of the

completed drug accountability log to the Novartis monitor or to the Novartis address provided in the investigator folder at each site.

### 5.5.3.2 Handling of additional treatment

At physician’s discretion, vitamin D and calcium supplementation may be managed by diet alone, and this should be recorded in the source records.

When dietary supplements are recommended, this non-study treatment has to be recorded in the Concomitant medications/Significant non-drug therapies eCRF, specifically:

- Calcium supplements at the time of infusion (all patients)
- Multivitamins that contain the RDA for calcium and vitamin D from Visit 1 to Visit 8 in line with [Table 5-1](#)
- Calcium or calcium plus vitamin D supplements from Visit 1 to Visit 8 in line with [Table 5.1](#)
- Vitamin D as a single supplement from Visit 1 to Visit 8 in line with [Table 5.1](#)

Details are described in the CRF completion guidelines.

### 5.5.4 Instructions for prescribing and taking study treatment

All kits of study treatment assigned by the IRT will be recorded/databased in the IRT.

Patients will receive a single dose of zoledronic acid or placebo of 0.05 mg/ kg, administered as a slow infusion of 100 mL over at least 30 minutes, at Visit 2 and Visit 5 as follows:

AGE	DOSE of ZOLEDRONIC ACID	TIME OF INFUSION
≥ 5 years to ≤ 17 years	0.05 mg/kg diluted in 100 mL of NS	30 minute infusion

The zoledronic acid or placebo dose is not to exceed 5.0 mg

A peripheral intravenous line must be used for the ZOL or placebo infusion. The i.v. infusion will be preceded by and followed by a 10 mL normal saline flush of the intravenous line.

As an example, the following table demonstrates how to prepare drug for a patient who weighs 46 kg.

**Table 5-2 Preparation of iv zoledronic acid or placebo infusion**

Patient Weight (kg)	Patient dose based on 0.05 mg/kg	Total number of 5.0 mg/100mL vials	Volume of ZOL or placebo to add to the normal saline	Volume of normal saline	Total volume of prepared infusion
46 kg	Y = 2.3 mg	1 vial	46 mL	100 mL	146 mL
X kg	X kg * 0.05 mg/kg = Y or Patient dose	1 vial	Y / 5mg/100mL = Patient dose	100 mL	100 mL + volume of reconstituted ZOL or placebo to add

Note: The maximum dose is 5 mg therefore the maximum volume from the 5mg/100mL ZOL/placebo vial to be used in this study is 100mL

## **Preparing the patient for the infusion**

In the event of a recent fracture, at least 1 month should elapse between the fracture and infusion of study drug. In the event of surgery to bone, at least 3 months should elapse between the procedure and infusion of study drug.

Before the first infusion of study treatment, both the local ionized calcium and serum creatinine should be within normal limits. Further details are provided in the Trial Master File.

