
1 V1 lab results, including GFR should be available prior to V2
 
2 All randomized patients will have limited blood chemistry assessments, GFR & urinalysis performed at Visit 3 (10 days after Visit 2) and Visit 6 (10 days after Visit 5). An optional repeat at V2 is included, if the time between screening and V2 is close to 4 weeks.
 
3 Test to be performed for females with childbearing potential only. Serum test for central laboratory at screening and final visits, local urine test prior to infusion at Visits 2 and 5 – if positive, infusion should not be started.
 
4 Screening DXA and X-rays should be performed at Visit 1 to ensure the central imaging laboratory can provide status on patient eligibility; these assessments should be performed early in the screening process.
 
5 Ionized Ca measured pre-dose (local lab) only before the first infusion, if below normal range, treat and repeat test before study drug infusion, if visit needs to be re-scheduled inform the monitor.
 
6 Lumbar spine, total body and [REDACTED]
 
7 Lateral thoracolumbar spine and posteroanterior (PA) left hand/wrist (for bone-age assessment and cortical bone thickness)
 
8 Including an oral examination for exposed bone. At screening visit the PI will perform an oral exam and , if needed, will refer the patient to a dentist
 
9 For exclusion purposes if increase between Visits 1 and 2 greater than 0.5 mg/dL (44.2 µmol/L).
 
10 Pain is assessed using Faces Pain Scale-Revised (FPS-R)
 
11 An AP (anteroposterior) spine X-ray will be employed at screening, in order to identify fractures that may not be readily visualized on the lateral spine because of rotation/scoliosis/other
 
[12 Only sites where additional safeguards required: Supervised urine pregnancy test]
 
 	
 
15 SAEs only to be collected from signing informed consent
 
16 Pulse rate and blood pressure only
 
17 Urine collection for PK: either an overnight sample, or collected over at least 4-hours during the day, for details, see Lab Manual
 
18 Screening visit can be on different days to permit scheduling of all investigations during the 28-day screening period
 
T = Telephone visit, S = Source documentation, D = Database, GC = Glucocorticoid, TD = study treatment discontinuation, PSW = Premature patient withdrawal
																	

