## 6.5.4 Laboratory evaluations

A central laboratory will be used for analysis of all specimens collected except for ionized calcium and serum creatinine (for exclusion purposes). Details on the collections, shipment of samples and reporting of results by the central laboratory are provided to investigators in the laboratory manual.

Clinically notable laboratory findings are defined in [Appendix 1](#).

EMLA cream may be used at all blood draws. EMLA Cream is a topical anesthetic which numbs the skin and decreases the sensation of pain. There should be up to three attempts to obtain a serum sample from the patient at any blood draw.

A central laboratory will collect and evaluate blood and urine samples for hematology, biochemistry and urinalysis at screening (Visit 1), Month 6 (Visit 5) and Month 12 (Visit 8).

A repeat at Visit 2 may be needed if the time between screening and Visit 2 is close to or more than 4 weeks and/or the Visit 1 result was close to the limits of the normal range.

Patients with laboratory tests containing clinically significant abnormal values will be followed regularly until the values return to normal ranges or until a valid reason for the abnormality, other than study drug related adverse event, is identified.

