### 6.5.4.2 Clinical chemistry

Non-fasting specimens will be obtained for glucose, creatinine, serum urea, uric acid, total protein, SGOT (AST), SGPT (ALT), alkaline phosphatase, sodium, potassium, chloride, phosphorus, magnesium, albumin, and calcium.

Specialized (non-fasting) testing for serum 25-hydroxy vitamin D will be performed at screening (Visit 1) and Month 12 (Visit 8).

Glomerular Filtration Rate (GFR) will be calculated using the Schwartz formula at all visits where serum creatinine will be measured (Visits 1, 3, 5, 6 and 8) by the central laboratory.

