### Schwartz Formula to calculate Glomerular Filtration

$$\text{GFR (mL/min/1.73 m}^2\text{)} = k [\text{Height (m)}] / \text{Serum Creatinine (mg/dL)}$$

k = Constant

k=0.41

Additional renal and calcium monitoring will be performed 10 days after each study drug infusion (Visit 3 and Visit 6).

Local laboratory evaluation of serum creatinine will be performed at Visits 1 and 2, if there is an increase greater than 0.5 mg/dL (44.2  $\mu\text{mol/L}$ ), the patient should be excluded.

Serum ionized calcium will be evaluated in the local laboratory at pre-dose (first infusion). If the result is close to or below the lower limit of the normal range, the infusion must be delayed until the value has returned to normal.

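### No creatinine or GFR result has to be read before the second infusion, although one is required before the first, so dose 2 may be given on a Day 10 renal result

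*Protocol*

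**What the plan says.** **Before dose 1 (Visit 2, Day 1).** Three renal checks apply.
- Table 6-1, footnote 1: "V1 lab results, including GFR should be available prior to V2".
- Section 5.5.4, on preparing the patient: "Before the first infusion of study treatment, both the local ionized calcium and serum creatinine should be within normal limits". The next sentence refers to the Trial Master File for further details.
- Sections 4.2 and 6.5.4.2: a creatinine rise of more than 0.5 mg/dL between Visits 1 and 2 excludes the child.

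**Before dose 2 (Visit 5, Day 180).** Section 6.5.4.2 confines the local test to the entry visits: "Local laboratory evaluation of serum creatinine will be performed at Visits 1 and 2". GFR is calculated at the visits "where serum creatinine will be measured (Visits 1, 3, 5, 6 and 8) by the central laboratory". Section 6.5.4 confirms where the Visit 5 sample goes: "A central laboratory will be used for analysis of all specimens collected except for ionized calcium and serum creatinine (for exclusion purposes". Central reporting arrangements are left to the laboratory manual. The SAP repeats the central visit list and adds no dosing rule.

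**Around both doses.** Section 6.5.4.2 adds post-dose sampling: "Additional renal and calcium monitoring will be performed 10 days after each study drug infusion (Visit 3 and Visit 6". Section 6.5.4 provides for follow-up: "Patients with laboratory tests containing clinically significant abnormal values will be followed regularly until the values return to normal ranges". Section 5.6.2 requires treatment to stop for renal failure, or for laboratory abnormalities that the investigator judges prohibitive.

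**The concern.** Both infusions give the same mg/kg dose of a drug that section 3.6 describes as excreted by the kidney and able to injure it. That section advises care in renal insufficiency and names regular renal monitoring as a mitigation. It does not limit the renal risk to the first dose, and no section explains why renal function is checked before dose 1 but not before dose 2.

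The laboratory stopping rule in section 5.6.2 can act only on a result that someone has read. Dose 2 is the last dose, so a Visit 5 abnormality reported after the infusion can prompt follow-up but cannot prevent exposure. A site that follows the protocol exactly could therefore give that dose to a child whose renal function has declined without symptoms since Day 10.

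**Working it through.** The plan states no figure on this point, so the check sets the schedule against the two infusion visits.

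**1. Renal samples up to dose 2** (Table 6-1; sections 6.5.4 and 6.5.4.2)

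| Visit | Day | Renal sample | Result required before an infusion? |
|---|---|---|---|
| 1 | -28 | central and local | yes, before dose 1 |
| 2 (dose 1) | 1 | local; central repeat optional | yes, local result before dose 1 |
| 3 | 10 | central | no rule stated |
| 4 | 90 | none (telephone visit) | not applicable |
| 5 (dose 2) | 180 | central, same visit as the infusion | no rule stated |

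**2. Age of the latest scheduled result in hand at dose 2**
- If the Visit 5 central result is not back: Day 180 - Day 10 = 170 days. A missed Visit 3 would make it older.
- If a local creatinine is read at Visit 5: Day 180 - Day 180 = 0 days.

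The documents do not give the central turnaround time, so 170 days is what the written rules allow. It is not a statement of what every site would do.

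**3. Children concerned**
- Planned randomization is 92 at 1:1, so 92 / 2 = 46 on zoledronic acid. This is the upper limit for those exposed to drug risk at dose 2.
- The evaluable target of 82 (82 / 2 = 41 per arm) is not a lower limit. Section 5.6.2 says that stopping treatment is not study withdrawal, so a child can miss dose 2 and still be counted in the study.
- The documents give no rate of silent renal decline between Day 10 and Day 180, so no number harmed is estimated.

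**4. Blood volume if a local creatinine is added** (Appendix 3; non-Australian volumes, serum pregnancy tests included)
- Visit 5 now: 3 + 3.5 + 3 = 9.5 mL. With the 2.5 mL local tube: 12.0 mL, below Visit 1 (14 mL) and Visit 8 (14.5 mL).
- Study total now: 14 + 8 + 3.5 + 9.5 + 3.5 + 14.5 = 53.0 mL. With the tube: 55.5 mL, a rise of 2.5 / 53.0 = 4.7%.

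**The case against.** The strongest reply is that the risk is small and largely covered already. Section 3.6 says bisphosphonate-induced acute kidney injury is undocumented in children. Section 3.3 reports no evidence of a long-term renal effect in a 155-patient pediatric trial that dosed quarterly, twice as often as here. Entry excludes a GFR below 60, nephrotoxic drugs are prohibited, and a data monitoring committee reviews safety. The Day 90 call collects adverse events, Visit 5 includes a physical examination, and section 11 allows extra safety tests. This stands. It limits the point to silent decline after Day 10, but none of these provisions requires a renal result to be read before dose 2.

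A second reply is that the dose 1 checks serve eligibility. That is fair for the creatinine-rise criterion and largely so for the Visit 1 results. It does not fit the sentence in section 5.5.4, which is written as a condition for infusing.

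Third, the Trial Master File or laboratory manual may already hold a Visit 5 rule, or a turnaround time that settles the matter. This cannot be excluded.

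A reader might also infer more than the documents support:
- That renal function is not tested at Visit 5. It is; what is missing is a rule to read the result first.
- That an abnormal Day 10 result would be ignored. Section 6.5.4 requires clinically significant values to be followed.
- That every second dose rests on a 170-day-old result. The Visit 5 result may be back in time; the text is silent either way.
- That calcium is the same oversight. Sections 3.1 and 5.1.2 show a deliberate choice to test ionized calcium before the first infusion only, with the concern centred on that infusion.

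**Conclusion.** The point holds as a low-probability safety gap. The protocol requires renal results to be in hand before the first infusion and requires none before the second. Under the written rules the latest scheduled result in hand at dose 2 can be 170 days old. At most 46 children on zoledronic acid are concerned, fewer after dropout or treatment discontinuation, with no firm lower bound.

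This rests on two assumptions: that neither the Trial Master File nor the laboratory manual sets a pre-Visit 5 renal rule, and that the Visit 5 central result is not routinely back before dosing. If either fails, what remains is a request to put the rule into the protocol. The change is worth making because it costs little. The documents do not show that harm is likely.

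**What to change.** - **Table 6-1 and section 5.5.4:** add a local serum creatinine at Visit 5, read before the infusion. The local creatinine at Visit 2 is the precedent, and the pre-infusion urine pregnancy test (Table 6-1, footnote 3) shows that a pre-dose condition already operates at Visit 5.
- **Limits:** use those the protocol already has, unless the sponsor's clinicians choose others: creatinine within normal limits, GFR not below 60 mL/min/1.73 m2, and a rise from baseline of no more than 0.5 mg/dL. If sites are to calculate GFR, check the height unit in section 6.5.4.2 first. As printed (metres, k = 0.41), a GFR of 60 at the lowest Appendix 1 creatinine limit of 0.2 mg/dL would need a height of 60 x 0.2 / 0.41 = 29 m.
- **Action:** state that the infusion is postponed while the result is abnormal or pending. Section 6 already allows visits as close as possible to the designated day.
- **Section 5.5.5:** this bars treatment interruptions, so add that a short safety delay is not a prohibited interruption.
- **If a rule already exists** in the Trial Master File or laboratory manual, move it into the protocol.

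The cost is amendment wording, one 2.5 mL tube per child at a visit that already has a blood draw, a same-day wait for families, and possibly a few second infusions delayed by days. Drawing the central sample a few days earlier would also work, but it means an extra trip for some families and possibly a second needle stick.

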### **5.5.5 Permitted dose adjustments and interruptions of study treatment**

Investigational or other treatment dose adjustments and/or interruptions are not permitted.

### **5.5.6 Rescue medication**

Not applicable.

### **5.5.7 Concomitant medication**

The investigator must instruct the patient to notify the study site about any new medications he/she takes after the patient was enrolled into the study. All medications, procedures and significant non-drug therapies (including physical therapy and blood transfusions) administered after the patient was enrolled into the study must be recorded in the concomitant medications / significant non-drug therapies eCRF.

Each concomitant drug must be individually assessed against all exclusion criteria/prohibited medication. If in doubt the investigator should contact the Novartis medical monitor before randomizing a patient or allowing a new medication to be started.

#### **5.5.7.1 Treatment of study drug related adverse events:**

As with other bisphosphonates, zoledronic acid has been associated with post-dose symptoms that may include fever, nausea, myalgia, arthralgia and bone pain, with onset occurring within the first 72 hours after the infusion. Typically these symptoms occur with the first infusion of bisphosphonate. The symptoms are usually mild to moderate and rarely severe. These symptoms may be adequately managed, at the discretion of the investigator, with non-steroidal anti-inflammatory agents (e.g. acetaminophen/paracetamol or ibuprofen) and/or anti-emetics by local treatment standards and according to approved local labeling. Based on data from controlled trials, treatment with non-steroidal anti-inflammatory agents will reduce the incidence of these symptoms by approximately 50%. In managing these symptoms it is important to encourage adequate hydration and food intake.

All dosages prescribed and dispensed to the patient and all dose changes during the study must be recorded on the concomitant medications/significant non-drug therapies CRF after start of study treatment.

### **5.5.8 Prohibited medication**

Use of the following treatments is NOT allowed throughout the duration of the trial: bisphosphonates, denosumab, high dose sodium fluoride and nephrotoxic drugs e.g. methotrexate.

### **5.5.9 Emergency breaking of assigned treatment code**

Emergency code breaks must only be undertaken when it is required to in order to treat the patient safely. Most often, study treatment discontinuation and knowledge of the possible treatment assignments are sufficient to treat a study patient who presents with an emergency condition. Emergency treatment code breaks are performed using the IRT. When the investigator contacts the system to break a treatment code for a patient, he/she must provide the requested patient identifying information and confirm the necessity to break the treatment code for the patient. The investigator will then receive details of the investigational drug treatment for the specified patient and a fax or email confirming this information. The system will automatically inform the Novartis monitor for the site and the Study Team that the code has been broken.

It is the investigator's responsibility to ensure that there is a dependable procedure in place to allow access to the IRT/code break cards at any time in case of emergency. The investigator will provide:

- protocol number
- study drug name (if available)
- patient number

In addition, oral and written information must be provided to the patient/parent/guardian on how to contact his/her backup in cases of emergency, or when he/she is unavailable, to ensure that un-blinding can be performed at any time.

